### **10.7** Other safety assessments

A dental and oral examination will be performed by a qualified dental health provider (minimum qualification: dentist) at screening (V1), V3 and V6 of the main study period, at V10 and at the-end-of-study visit (V18), or at the subject's last study visit if this is earlier. Results of dental and oral examination will be reported in terms of adverse events: findings indicating a worsening of the subject's condition since screening are to be recorded as adverse events.

Details are given in Appendices 16.4.1.

As part of the physical examination, particular attention will be paid to lungs in order to detect any signs of aspiration, at baseline and every subsequent visit.

#### C-SSRS

Prospective monitoring of suicidality with the Columbia-Suicide Severity Rating Scale [C-SSRS] should be considered the most important (but not the only) source of information concerning suicidality.

Suicidality will be assessed prospectively in subjects at baseline and every scheduled and unscheduled post-baseline site visit. The appropriate version of this scale ensures the consistent application of this important measure regardless of indication or investigator experience with the subject matter. With C-SSRS in place, administration of this semi-structured clinician-based assessment scale is standardized. The C-SSRS quickly and efficiently identifies those subjects that require additional clinician follow-up.

Following versions of the C-SSRS are to be applied only for newly recruited patients:

- 1. Children's baseline / screening version
- 2. Children's since last visit version.

The C-SSRS interview should only be assessed with children of respective age and cognitive state. Clear age cut-offs for the C-SSRS were not defined by the authors, but it has been found that administration is possible in general for children with a developmental age of about 7 years. Otherwise it should be documented in the electronic Case Report Form (eCRF) that a child was not able to assess the C-SSRS at a respective visit.

The C-SSRS is based on the research and development at the Columbia University by Posner et al. [Posner 2007a] supported by Columbia-Classification Algorithm for Suicide Assessment (C-CASA) developed by the same group [Posner 2007b]. It is a semi-structured clinical interview consisting of domains of suicidal ideation, suicidal behavior and non-suicidal self-injurious behavior, and details of actual and potential lethality. It is designed for personal interview administration. Subjects or Parents/Caregivers are asked directly by a trained clinical assessor. Clinical assessment questions are presented, and subjects provide their responses. These responses enable the interviewer to branch to the appropriate follow-up questions, faithfully adhering to C-SSRS probing specifications and potential positive responses. This approach provides consistent assessment and documentation.

At the end of the assessment the subject should not be released from the study center until the results of the C-SSRS (positive or negative) are reviewed and the subject is not considered to be at risk. If there is doubt about whether a subject is at risk, the Investigator should obtain appropriate psychiatric consultation.

# **11** DATA QUALITY ASSURANCE

Inspections by regulatory authority representatives and IECs/IRBs are possible at any time, even after the end of the study. The investigator is to notify the sponsor immediately of any such inspection. The investigator and institution will permit study-related monitoring, audits, reviews by the IEC/IRB and/or regulatory authorities, and will allow direct access to source data and source documents for such monitoring, audits, and reviews.

The sponsor is also to be notified immediately of any inspection foreseen at third-party vendors (e.g. inspection of investigation sites or a CRO by national authorities).

### **11.1 Standardization procedures**

Standardization procedures will be implemented to ensure accurate, consistent, complete, and reliable data, including – but not limited to – methods to ensure standardization among sites (e.g., training, newsletters, investigator meetings, monitoring, central laboratories, centralized evaluations, and validation methods).

This study will be monitored regularly by a qualified monitor from the CRO according to GCP and ethical guidelines and the respective SOPs (see Section 11.4).

#### **11.2** Source documentation requirements

All data collected from a subject during the course of a clinical study are to be entered and/or filed in the respective subject file. This includes a copy of the letter sent to the subject's primary physician about the subject's participation in the study (provided the subject has a primary physician and has agreed to the primary physician being informed). The subject's file must also contain a descriptive statement on the informed consent procedure (see Section 3.3.2). The site will keep a source data location list which will outline for the different data categories (e.g. demographics, medical history, and adverse events etc.), including electronic data, which document serves as source for this data (e.g. subject file, laboratory report).

If the subject has no medical history on file at the study site, every attempt (e.g. by letter, e-mail, phone) should be made to obtain the following data by means of a doctor's letter, in order to verify the fulfillment and non-fulfillment of inclusion and exclusion criteria. These attempts are to be documented in the subject file.

Study sites will use a sponsor-validated, web-based electronic case report form [eCRF], and study data will be entered on a secure on-line basis by authorized study-site personnel.

If a study site is using an electronic system for documenting source data, a member of the site staff must print out the source data after each visit. The paper print-outs must be

overlapping, if possible (i.e., must contain at least the last row of data from the subject's previous visit). If it is not possible to obtain overlapping paper print-outs, the completeness of source data must be ensured by other suitable means, such as printing by sequential date order. The print-out must be signed and dated by a member of the site staff who can confirm the accuracy and completeness of data in the paper print-out. The monitor should also sign and date after verifying the source data. The paper print-out should be stored in the ISF. If source data information is entered retrospectively, this must be done directly on the paper print-out and should be initialed and dated. The same applies to corrections of any paper-based data.

If the site is using a validated computer system including audit trail with a separate access for the monitor (i.e., the monitor can only access the data of the study subjects), then no such paper print-outs are required.

## 11.3 Data management

Authorized members of the investigator's staff will enter the information required by the protocol into the web-based eCRFs (electronic data-capture [EDC] system (EDC)) provided by Merz Pharmaceuticals/

All persons who are to enter data into the eCRF will be trained by using an e-learning tool and support from a member of the CRO if necessary. After the successful completion of the training, all participants will receive a training certificate. Access to the e-learning tool and to the eCRF will be password-controlled. Passwords must be kept securely and be individual to each member of staff, and must not be shared with or used by anyone else.

Plausibility checks will be performed according to a data validation plan. Inconsistencies in the data will be queried to the site via the web-based eCRF; answers to queries or changes to the data will be documented in the eCRF directly by an authorized member of the investigator's staff. The audit trail in **documents** all changes. Edit checks trigger automatic queries during data entry when a field is not populated according to the specifications set out in the data validation plan. Manual queries (to be answered by site staff) can be raised during source data verification or during medical, safety or data management review.

Laboratory data will be received electronically and merged with the eCRF data (but not uploaded into the EDC system). Plausibility checks will be performed to ensure correctness and completeness of these data. Abnormal results will be reported to the investigator in a timely manner for review and treatment if necessary to ensure the subject's well-being during the research.

The sponsor's data management function team will be responsible for data-processing, in accordance with the sponsor's data management procedures and all applicable laws. No identifiable data will be processed. After all data have been entered and all queries solved, the data base will be closed. After database closure, unblinding will take place. If

there are any changes to the data after data-base closure, these changes will be documented according to the relevant SOP.

The results of the semi-structured interview will be documented by using the paper version of the C-SSRS and the data will be entered into the eCRF. Plausibility checks will be performed to ensure correctness and completeness of these data.

## 11.4 Monitoring

This study will be monitored regularly by a qualified monitor from the CRO according to GCP guidelines and the respective SOPs. Monitoring procedures include one or more visits designed to clarify all prerequisites before the study commences. Interim monitoring visits will take place on a regular basis according to a mutually agreed schedule. During these visits, the monitor will check for completion of the entries on all the eCRFs; for compliance with the clinical study protocol, ICH GCP principles, the Declaration of Helsinki, and regulatory authority requirements; for the integrity of the source data with the eCRF entries; and for subject eligibility. Monitoring also will be aimed at detecting any misconduct or fraud. Risk-based monitoring will not be used for this study because of the vulnerable nature of the study participants.

In addition, the monitor will check whether all AEs and SAEs have been reported appropriately within the time periods required.

The investigator and all staff will be expected to cooperate with the monitor by providing any missing information whenever possible. The investigator must be available to answer questions arising during regular monitoring visits. In addition, the investigator is required to:

- Have all data properly recorded in the eCRF and subject files before each monitoring visit.
- Have the source documentation available at the monitoring visits.
- Record all IP dispensed in the eCRF and the drug inventory records.

All subjects who are screened, but not entered into the study, will be listed on the subject screening/enrollment log according to local confidentiality requirements – for example by initials and date of birth.

Further details of monitoring activities will be set forth in the monitoring manual.

### 11.5 Auditing

Audits will be performed according to the corresponding audit program, including the possibility that a member of the sponsor's quality assurance function team may arrange to visit the investigator in order to audit the performance of the study at the study site, as

well as all study documents originating there. Auditors conduct their work independently of the clinical study and its performance.

Audits may also be performed by authorized contract auditors. In this case, the sponsor's quality assurance function manager will agree with the contract auditor regarding the timing and extent of the audit(s). In case of audits at the investigational site, the monitor will usually accompany the auditor(s).

## **12** STATISTICAL METHODS

This section describes the statistical analyses foreseen at the time of study planning. Further details on the statistical and analytical aspects will be presented in the Statistical Analysis Plan [SAP].

Any deviations from planned analyses, the reasons for such deviation, and all alternative or additional statistical analyses that may be performed before database close or unblinding, respectively, will be described in amendments to the clinical study protocol or the SAP. All deviations and/or alterations will be summarized in the clinical study report.

Note that the groups of

- subjects in age group 6–17 years treated with active treatment or placebo and
- subjects in age group 2-5 years treated with active treatment only

will be analyzed separately.

#### 12.1 Determination of sample size

A total of 249 subjects is planned to be enrolled. Of these, at least 219 children and adolescents are planned to be enrolled in the age group 6–17 years, which will form the population for the primary efficacy analysis. In the main period, this group of children/adolescents will be randomized with a randomization ratio of 2:1, i.e. 146 subjects will receive NT 201 and 73 subjects will receive placebo. At least 30 children in the youngest age group 2–5 years are planned to be enrolled and treated open-label with active treatment only.

#### 12.1.1 Safety

#### Subjects in age group 6-17 years

To generate a database with long-term safety data large enough to fulfill the requirements set out in the ICH E1 guideline (at least 100 subjects treated over one year) and taking into account an anticipated drop-out rate at least 144 subjects have to be included in the NT 201 group.

#### Subjects in age group 2-5 years

A total of 30 subjects in the youngest age group are assumed to be a sufficiently large database to generate a safety profile for this patient group.

### 12.1.2 Efficacy

Subjects in age group 6-17 years

The sample size of 219 subjects is sufficient to provide 95% power to detect a statistically significant difference in means of 1.0 point between active treatment-treated and placebo-treated subjects with a standard deviation of 1.93 points (two-sided *t* test, significance level  $\alpha = 0.05$ ).

#### Subjects in age group 2-5 years

Since the primary efficacy analysis is based on the population of subjects aged 6–17 years, no formal sample size estimation is necessary for the subjects in the youngest age group (2–5 years) who all receive active treatment. Additionally, only the co-primary efficacy variable 'GICS four weeks after injection' is assessed in this population. Power calculations with respect to the GICS four weeks after injection show that the sample size of 30 subjects is sufficient to detect a GICS of  $\pm 2.0$  points as a statistically significant difference to a GICS of 0 points (no change) at Week 4 (V3) with a power of 95% by assuming a standard deviation of 2.94 points (two-sided *t* test, significance level  $\alpha = 0.05$ ).

#### 12.2 Analysis sets

The following analysis sets will be defined for the statistical analysis of the main period:

#### Safety evaluation set MP

The safety evaluation set [SES] of the main period is the subset of all subjects who received study medication (NT 201 or placebo) during the main period of the study.

#### Full analysis set

The full analysis set [FAS] is identical to the subset of subjects in the SES (MP).

#### Per protocol set

The per protocol set [PPS] is the subset of subjects in the FAS aged 6-17 years without major deviations from this protocol. Major protocol deviations will be defined during the blind data review meeting at the end of this study.

For the OLEX period, the following analysis set is defined:

#### Safety evaluation set OLEX

The safety evaluation set [SES] of the OLEX period is the subset of all subjects who received study medication (NT 201) at least once during the OLEX period of the study.

### 12.3 Variables for analysis

### 12.3.1 *Efficacy variables*

#### 12.3.1.1 Primary efficacy variables

The following variables will be defined as primary and co-primary efficacy variables for the subjects aged 6–17 years:

- Change in mean uSFR from baseline (V2) to V3 [Week 4]. The mean uSFR is calculated by averaging the two assessments at each visit.
- GICS at V3 [Week 4] representing the functional improvement in drooling since baseline as assessed by the carer/parent(s).

#### 12.3.1.2 Secondary efficacy variables

The following secondary efficacy variables will be analyzed for the subjects aged 6–17 years:

- Change in mean uSFR from baseline (V2) to V4 and V5 [Week 8 and 12, respectively].
- GICS at V4 and V5 [Week 8 and 12, respectively].

Merz Pharmaceuticals GmbH MRZ60201\_3091\_1

#### SOP/245/EN - CLINICAL STUDY PROTOCOL Version 2.0 Version 16-JUN-2016

## 12.3.2 Pharmacodynamic variables

Not applicable.

### 12.3.3 Pharmacokinetic variables

Not applicable.

### 12.3.4 Pharmacogenetic variables

Not applicable.

### 12.3.5 Safety variables

#### 12.3.5.1 Primary safety variable

Occurrence of treatment emergent AEs [TEAEs] overall and by injection cycle.

#### 12.3.5.2 Secondary safety variables

- Occurrence of treatment emergent AESIs [TEAESIs] overall and by injection cycle.
- Occurrence of treatment emergent SAEs [TESAEs] overall and by injection cycle.
- Occurrence of TEAEs related to treatment as assessed by the investigator overall and by injection cycle.
- Occurrence of TEAEs leading to discontinuation overall and by injection cycle.

#### 12.3.5.3 Other safety variables

• The number of subjects with suicidal ideation, suicidal behavior, and self-injurious behavior without suicidal intent during treatment based on the C-SSRS.

#### 12.3.6 Other variables

The following additional variables will be analyzed:

- Vital signs (blood pressure, heart rate, body temperature) at screening (V1), baseline (V2), V3 [week 4], V6 [week 16], during the main period and at each injection visit in the extension period and at the end-of-study visit (V18) [Week 64].
- Body height and weight at screening (V1), final visit of the main period (V6) [Week 16], and end-of-study visit (V18) [Week 64].
- BMI, calculated from body weight and height, at screening (V1), final visit of the main period (V6) [Week 16], and end-of-study visit (V18) [Week 64].
- Clinical chemistry (including alkaline phosphatase [AP] and blood glucose [BG]) and hematology at screening (V1), final visit of the main period V6 [Week 16], and end-of-study visit V18 [Week 64].
- GMFCS level at baseline (V2) for CP patients.
- Occurrence of antibodies against BoNT-A in subjects with  $\geq$  30 kg BW.

#### 12.4 Statistical analysis methods

Full details of all analyses will be given in the SAP.

### 12.4.1 *Efficacy variables*

All efficacy analyses on data from the main period will be based primarily on the FAS and where deemed sensible additionally, for sensitivity purposes, on the PPS. Analyses on data from the extension period are based on the SES only. If not stated otherwise, analyses are performed by all age groups and treatments. Statistical tests will be two-sided hypothesis tests for between-treatment differences in general. Continuous variables (values and changes from baseline) will be summarized by N, mean, standard deviation, median, quartiles, minimum, and maximum. For qualitative variables, absolute and percent frequencies (N, %) and, if applicable, shift tables will be displayed. Confidence limits and descriptive p-values will be given, where appropriate.

### 12.4.1.1 Primary efficacy variables

The primary efficacy analysis will be performed on the group of subjects within the FAS aged 6–17 years. A mixed model repeated measurement analysis (MMRM, 2-sided, significance level alpha=0.05) with comparison of least square means between NT 201 and placebo will be used for the confirmatory analysis of the co-primary efficacy variables. The dependent variables will be the change in uSFR from baseline (V2) to V3 [Week 4] and the carer's/parent's GICS at V3 [Week 4], respectively. The independent variables are defined as treatment group, pooled investigation sites and age groups as fixed factors, visit\*treatment as interaction term, and visit as repeated factor. To adjust for the baseline status, the MMRM of the uSFR change additionally includes the baseline score of the uSFR as covariate. Since no baseline assessment of the GICS is available, the baseline mTDS rated by the parent(s)/carer is used as covariate in the MMRM model for the GICS. Only if both co-primary efficacy variables show a statistically significant difference compared to placebo the superiority of NT 201 over placebo will be considered to be proven. Therefore, no  $\alpha$ -adjustment for multiple testing is necessary.

Sensitivity analyses will be performed using the same approach on the PPS.

In order to investigate the impact of missing values and different approaches for handling of missing data, sensitivity analyses will be performed on the FAS (age 6-17 years) and on the PPS using the baseline observation carried forward approach (BOCF, no effect) for uSFR while imputing missing GICS entries at week 4 as "no change" and without missing replacement (observed case analysis). For this purpose the MMRM model as described above will be adapted as an analysis of covariance (ANCOVA) model without visit\*treatment as interaction and without visit as repeated factor.

Furthermore, a non-parametric Wilcoxon rank-sum test will be performed as sensitivity analysis of the co-primary efficacy variables to investigate the impact of potential deviations from the assumption of normal distribution. The test will be performed for FAS (age 6-17 years) and PPS using observed cases as well as using BOCF for uSFR and imputing "no change" for GICS.

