#### 9.1.1.2 *Efficacy assessments*

The following efficacy assessments will be used to compare the efficacy of the active treatment (NT 201) with that of placebo. Details of these assessments are given in the appendices to this protocol Appendix 16.3.

• Unstimulated salivary flow rate [uSFR] (weighing of two absorptive swabs soaked with saliva over five minutes; procedure repeated once after 30 minutes [±5 minutes]) for all randomized subjects.

• Global Impression of Change Scale [GICS] of functioning as a result of treatment from last injection on a 7-point scale by carer/parent(s) and subject in a combined rating.

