Only if both co-primary efficacy variables show a statistically significant difference compared to placebo the superiority of NT 201 over placebo will be considered to be proven. Therefore, no  $\alpha$ -adjustment for multiple testing is necessary.

Intercurrent events with potential bias on the co-primary endpoints will be identified prior to or during the BDRM. In case these events are judged as relevantly biasing the co-primary endpoints, conservative sensitivity analyses on the MMRM model will be specified during the BDRM.

In addition to the MMRM, an analysis of covariance (ANCOVA) model will be performed on the FAS (age 6-17 years) using observed cases as well as using the baseline observation carried forward approach (BOCF, no effect) for uSFR and imputing missing GICS entries as "no change". The ANCOVA models will be performed by use of the following SAS code:

```
proc mixed data = dataset;
  class treatment pooled_site age_group;
  model AuSFR (GICS) = treatment pooled_site age_group uSFR_baseline
        (mTDS)/solution ddfm=kr;
  LSMeans treatment pooled_site age_group / pdiff CL alpha = 0.05;
  where visit = V3;
run;
```

Furthermore, a non-parametric Wilcoxon rank-sum test will be performed as sensitivity analysis of the co-primary efficacy variables to investigate the impact of potential deviations from the assumption of normal distribution. The test will be performed for FAS (age 6-17 years) using observed cases as well as using BOCF for uSFR and "no change" for GICS. The Wilcoxon rank-sum test will be performed by use of the following SAS code:

```
proc npar1way data=dataset wilcoxon;
  class treatment;
  var ΔuSFR;
run;
```

For the GICS, a logistic regression will be performed as sensitivity analysis to the distribution assumption. The responder rate will be determined, i.e. all subjects with GICS entry of at least +1 (Minimally improved).

Treatment arm comparisons with respect to responders based on the GICS entries will be performed analogously to the primary efficacy analysis, but based on estimates of logistic regression models. The dependent variable of these models will be the response to treatment. Treatment group, pooled investigation site and age group will be included as factors into the models. Baseline adjustment will be done by including the baseline values of the mTDS as covariate. The following SAS code will be used for estimation:

```
proc logistic data=dataset desc order=formatted;

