# 7.7.5 Examination of Subgroups

All subgroup analyses will be performed on an explorative level.

Tables with descriptive statistics for uSFR, GICS, GICS response and mTDS will be repeated for the following subgroups:

- Age group:
  - o 6-9 years,
  - o 10-12 years
  - o 13-17 years.
- Pooled investigational sites (where pooling will be the same as used for the MMRM and ANCOVA models).
- Etiology (cerebral palsy, traumatic brain injury and other)
- Gender
- Weight group (rounded to one decimal place):
  - ]0, 30 kg[ and  $\ge$  37.5kg (corresponds to a planned NT201 exposure of  $\le$  2U/kg)
  - $\circ$  [30, 37.5kg[ (corresponds to a planned NT 201 exposure of > 2U/kg)
- Baseline disease severity:
  - $\circ$  uSFR at baseline  $\leq$  median of uSFR at baseline
  - uSFR at baseline > median of uSFR at baseline

These analyses will be performed for FAS, PPS and SES OLEX for uSFR and GICS. Tables for mTDS will be created for FAS and SES OLEX. The analysis by age group will be performed for FAS (6-17 years) instead of FAS.

In addition, the following uSFR and GICS MMRM models will be built:

- 1. MMRM model with treatment, pooled site and age group included as (fixed) factors and uSFR at baseline (or mTDS at baseline) included as covariate, visit\*treatment and subgroup\*visit\*treatment as interaction terms and visit as repeated factors. I.e. two different models will be calculated (pooled site as interaction term and age group as interaction term).
- Primary endpoint MMRM model based on subjects with uSFR at baseline ≤ median of uSFR at baseline, only.
- 3. Primary endpoint MMRM model based on subjects with uSFR at baseline > median of uSFR at baseline, only.
- 4. MMRM model with treatment, pooled site, age group, etiology, gender, weight group included as (fixed) factors and uSFR at baseline (or mTDS at baseline) included as covariate, visit\*treatment and subgroup\*visit\*treatment as interaction terms and visit as repeated factors. I.e. five different models will be calculated (pooled site as interaction term, age group as interaction term, etiology as interaction term, gender as interaction term and weight group as interaction term).

For each subgroup level of age group and pooled site, the LS-Mean for difference between NT201 and placebo at week 4 will be selected from Model 1) and presented in a table and forest plot.

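### The GICS co-primary MMRM and ANCOVA could also adjust for baseline uSFR, which is already collected; leaving it out is not an error, and the likely gain is small

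*Protocol*

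**What the plan says.** Protocol 12.4.1.1 and SAP 7.1.1 give both co-primary models the same core: treatment, pooled site, age group, visit and visit-by-treatment. Each model then receives one baseline covariate. The uSFR model takes baseline uSFR. For GICS, which has no baseline, "the baseline mTDS rated by the parent(s)/carer is used as covariate in the MMRM model for the GICS". The SAP code for the MMRM and the ANCOVA writes the two covariates as alternatives, one per model. For the GICS responder logistic regression, SAP 7.1.1 says "Baseline adjustment will be done by including the baseline values of the mTDS as covariate". Baseline uSFR is therefore a covariate in no confirmatory or sensitivity model for GICS, and neither document says why.

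The measurement is available. Protocol 9.1.1.2 describes it as "weighing of two absorptive swabs soaked with saliva over five minutes; procedure repeated once after 30 minutes" and applies it to all randomized subjects. SAP 7.1 and 7.7.1 replace a missing Visit 2 value with the last valid value before the first injection.

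SAP 7.7.5 lists baseline uSFR, split at its median, under baseline disease severity. It announces that "In addition, the following uSFR and GICS MMRM models will be built", and Models 2 and 3 fit the primary MMRM separately at or below, and above, that median.

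**The concern.** Both co-primary variables must be significant for superiority to be claimed, so GICS alone can decide the trial. A prognostic baseline variable left out of a linear model stays in the residual. If baseline flow predicts Week 4 GICS beyond mTDS, site and age, the standard error is somewhat larger than it need be. The estimate then also moves with any chance imbalance in flow between the 146 and 73 children. The uSFR model adjusts for that imbalance directly. The GICS model does so only as far as mTDS, site and age track flow. The covariate is already measured, cleaned and used in the companion model, so using it for GICS needs no new data.

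**Working it through.** **Inputs.** From Protocol 12.4.1.1: "MMRM, 2-sided, significance level alpha=0.05". From Protocol 12.1 and 12.1.2: "The sample size of 219 subjects is sufficient to provide 95% power", 146 v 73, a "difference in means of 1.0 point between active treatment-treated" and placebo-treated subjects, and a "standard deviation of 1.93 points". The endpoint is not named; a scale in points implies GICS, since the SAP gives uSFR in g/min. No reduction of the SD for covariates is stated.

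**Step 1: reproduce the plan's figure.** The imbalance factor is √(1/146 + 1/73) = 0.1433. The SE is 1.93 × 0.1433 = 0.2767. Power by the normal approximation is Φ(1.0/0.2767 − 1.96) = Φ(1.65) = 95.1%; the noncentral t gives 94.9%. Solving for the sample size at 95% power gives 73 placebo and 219 in total. The plan's figure reproduces, and it does so without any covariate.

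**Step 2: add baseline uSFR.** Let r be the partial correlation between baseline uSFR and Week 4 GICS given mTDS, site and age. The documents do not give r, so it is an assumption and a range is shown. The residual SD becomes 1.93 × √(1 − r²). One extra estimated coefficient inflates the variance by about (219 − 3)/(219 − 4) = 216/215 = 1.0047.

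**Step 3: chance imbalance.** Under randomization, the difference in mean baseline uSFR between arms has an SD of 0.1433 in units of the covariate's own SD. A one-SD imbalance shifts the GICS difference by r × 1.93 × 0.1433.

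| r (assumed) | SE reduction, 1 − √(1 − r²) | Variance ratio after the penalty | Power at 1.0 point | Shift from a one-SD imbalance |
|---|---|---|---|---|
| 0 | 0% | 1.005 | 95.0% | 0 |
| 0.1 | 0.5% | 0.995 | 95.2% | 0.03 |
| 0.2 | 2.0% | 0.964 | 95.7% | 0.06 |
| 0.3 | 4.6% | 0.914 | 96.6% | 0.08 |
| 0.4 | 8.3% | 0.844 | 97.6% | 0.11 |
| 0.5 | 13.4% | 0.754 | 98.6% | 0.14 |

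Power is by the normal approximation and includes the penalty; noncentral t values are about 0.1 to 0.2 percentage points lower. At r = 0.3 the variance ratio of 0.914 is worth 219/0.914 ≈ 240 children, about 20 more than planned. An imbalance at the 95% limit (1.96 × 0.1433 = 0.28) would shift the difference by about 0.16 point at r = 0.3.

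**Limits of the check.** It treats the Week 4 contrast as a two-group comparison with a common SD and does not simulate the full MMRM. It also uses 1.93 as the SD left after mTDS, site and age, although the plan gives it for a plain t test. If those terms explain variance, the shifts are smaller, so they are upper values for each r.

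**The case against.** A single prespecified baseline covariate is a valid choice, and leaving out a second contradicts nothing in the plan. That stands in full. Several stronger readings are tempting, and the documents do not support them.

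- *The GICS analysis is biased or underpowered.* Randomization protects the comparison, the type I error is unaffected, and chance imbalance is already reflected in the standard error. The 95% power was computed from an SD with no covariate reduction.
- *The model adjusts for mTDS and nothing else, and uSFR is the trial's real severity measure.* Pooled site and age group are also fitted. The inclusion criteria define severe drooling by mTDS, so mTDS is a severity measure too. The carer's mTDS also comes from the same kind of rater as the GICS.
- *The entry threshold leaves mTDS too narrow to adjust with.* The threshold of 6 applies to the investigator's rating; the covariate is the carer's. No figure shows that the carer's rating is restricted.
- *SAP 7.7.5 contradicts the primary model.* Splitting by baseline uSFR examines whether the treatment effect is consistent. It does not assert that uSFR predicts GICS. Etiology, gender and weight group also appear in that section and are not in the confirmatory model either.
- *The gain is substantial.* A larger figure can be had by supposing a true difference of 0.75 point, where power would go from about 77% to 80.9% at r = 0.3. That difference is not in the plan.

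There is also reason to expect a small r. GICS rates change in functioning since the injection, not a level. Protocol 4.1.1 attributes most severe drooling in children to impaired tongue or bulbar control, not to excess saliva production.

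None of this argues against the linear-model change. At r = 0 the variance penalty is about 0.5% and the power loss about 0.1 percentage point.

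**Conclusion.** This is an optional, nearly free improvement to a valid analysis. Baseline uSFR is absent from the GICS MMRM and ANCOVA, it is collected in the whole randomized population, and no reason for its absence is given. If r lies between 0.1 and 0.3, adding it lowers the SE by about 0.5% to 4.6% before the one-degree-of-freedom penalty. It takes power at the planned difference from about 95% to between 95.2% and 96.6%. It also removes exposure to an imbalance shift of up to about 0.08 point (one SD, r = 0.3), against a planned difference of 1.0. All these sizes rest on the assumed r and on 1.93 as the residual SD. If r is near zero, nothing is gained and almost nothing is lost.

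The case covers the linear models only. In the logistic model the √(1 − r²) gain does not carry over: adding a prognostic covariate generally raises the SE of the log odds ratio and changes the conditional odds ratio being estimated. The SAP already allows for that model not being estimable.

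**What to change.** Before unblinding, by amendment to the protocol or SAP as Protocol Section 12 provides, add study-baseline uSFR as a second continuous covariate beside carer-rated mTDS in the GICS MMRM and ANCOVA (Protocol 12.4.1.1, SAP 7.1.1). Use the same baseline value as in the uSFR model, including its fallback for a missing Visit 2 measurement. Leave the logistic model and all other terms unchanged.

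The Week 8 and Week 12 GICS analyses and the per-protocol repeats follow the primary specification and would inherit the term. So would Models 2 and 3 of SAP 7.7.5, and the SAP should say so.

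If the sponsor prefers to keep the confirmatory model as it is, a prespecified sensitivity model with the extra covariate, or a sentence explaining the omission, would answer the point. After unblinding, the extra covariate could only be presented as post hoc.

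The cost is one model term, one degree of freedom (about 0.5% in variance if r = 0), no new data, and the loss from the GICS model of any child with no valid uSFR before the first injection.
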